- (1) *Discussion of Risks and Benefits of Opioid Analgesics as Long-Term Therapy for Patients with Chronic Pain and Establishment of a Treatment Goal.* This alert is triggered whenever a refill for a long-acting or extended-release opioid is entered or when any new opioid prescription is ordered.
- (2) *Evaluation of Risk Factors for Opioid-Related Harms.* This alert is triggered whenever there is an existing diagnosis of prior substance abuse disorder, history of overdose, history of sleep apnea, renal or hepatic insufficiency, age over 65 years, or a diagnosis of depression, anxiety disorder, or Post-Traumatic Stress Disorder in the setting of opioid use.
- (3) *High-Risk Opioid Co-Prescribing: Co-Prescribing of Benzodiazepines and Opioids.* This alert is triggered whenever an order for a benzodiazepine is entered in the setting of a preexisting opioid prescription, or vice versa.

Figure 2 presents a schematic demonstrating the process flow for a CDS alert, using the example of the co-prescribing alert. The process begins when a provider places the medication order in the EHR. The Choosing Wisely algorithm, powered by Stanson Health, a CDS developer used by Cedars-Sinai to power its EHR alerts (www.StansonHealth.com), then evaluates over 30 patient-level data elements to determine whether an alert should be triggered. If there is evidence of potentially inappropriate co-prescription, then the EHR displays a “pop-up” reminder with language supported by Choosing Wisely guidelines. The provider may override the alert by selecting one of several pre-populated reasons (e.g. “end-of-life care”) and the system records the rationale. The system also allows the provider to offer open-ended comments explaining the reason for override. Conversely, the provider may choose to cancel the order and back out from initiating a prescription. Through an analytics dashboard supported by Stanson Health and already used by our health system to monitor system performance with Choosing Wisely alerts, we will track: (1) which provider activated the alert, (2) whether the provider overrode the alert or canceled the order, and (3) for which patient

the alerts were triggered. In this manner, the system offers hard metrics that are already embedded and operating within our EHR data analytics system, offering real-time process measures for the CDS arm.

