Specific Health Decision the Comparator Is Intended to Inform: The Choosing Wisely CDS alerts directly address the question of whether continuing an opioid prescription is appropriate in patients with chronic pain, particularly for those individuals at high risk for drug-drug interactions, at risk for addiction, or for whom opioids may not be effective for long-term pain relief. The decision should include patient and provider discussion of medication risks and benefits.

Evidence of Widespread Use: The alerts powered by Stanson Health are already in use by more than 100 health care systems with more than 30,000 combined physicians. Other large healthcare systems such as Kaiser Permanente are currently using similar CDS systems to reduce inappropriate opioid prescribing for their more than 4 million members.⁷⁷

Evidence of Effectiveness: At Kaiser Permanente, the CDS-based alerts function very similarly to the alerts used at Cedars-Sinai: when a provider attempts to submit an order for certain high-risk opioid prescriptions, the EHR triggers an alert detailing the risks of the medication and offers links to evidence-based guidelines. Partly as a result of this intervention, prescriptions for oxycodone decreased at Kaiser Permanente by 70 percent in two years.⁷⁷ In a 10-week pilot study examining the effects of CDS alerts of benzodiazepine use in patients 65 years and older, a specific Choosing Wisely recommendation, Cedars-Sinai reduced prescriptions of benzodiazepines in the patient population by 32%.¹⁰⁴

2. CDS via PEAT.

Description: Consumer Reports Health, a patient advocacy organization, has created education materials aimed at patients with chronic pain. The patient education materials we selected for this study, **"Pain Management: Which Treatment is Right for You"** (Appendix I), include information about opioids along with alternatives to opioids, including nonsteroidal anti-inflammatory drugs (NSAIDs), aspirin and acetaminophen. Additionally, the materials present information about non-pharmacological treatments for chronic pain, many of which are recommended in recent CDC pain management guidelines.²⁰ The Consumer Reports education tool was informed by patient needs, is written with easy-to-understand language, and discusses the addiction risks, side effects and long-term effectiveness of opioids.

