E4.e. Data Collection (RQ-2). Upon auto-enrollment, we will extract the following variables from the electronic health record: chronic pain condition, length of time with chronic pain diagnosis, race and ethnicity, language, marital status, history of pharmacologic treatment, surgical history related to chronic pain condition, past injuries related to chronic pain condition, and length of time with current primary care provider¹³⁷. When the intervention period is initiated, all eligible patients who have any follow-up visits during this 12-month period in both study arms will be sent the questionnaires. We will also capture depression scores via the Patient Health Questionnaires -PHQ-2 and/or PHQ-9 in the EHR. Furthermore, to determine if conversations about opioid medications took place during the visit that was

informed by either the CDS or the PEATS, we will conduct a structured review of a random sample of charts from both study arms.

E5. Statistical Analysis

E5.a. Descriptive and Exploratory Analyses. We will use frequencies and means for univariate descriptive analyses. We will use chi-square tests and paired t-tests to determine whether there are differences between the two study arms; using these bivariate analyses, we will identify covariates and patient- and physician-level moderators to use in the regression models. We will also consult with our Patient Partner to ensure that all appropriate patient-level covariates are included in the final models.

E5.b. Multi-Variate Regression Models. To evaluate the effectiveness of the comparators on the selected outcomes, we will use hierarchical linear regression models to measure changes in the outcomes over time using growth modeling statistical techniques¹³⁸ and will adjust for clustering at the patient, provider, and provider office level. Growth modeling allows the testing of individual differences in outcomes over time. In this study, we will examine HRQOL and communication scores over 12 months for the two study arms. We will adjust for patient- and provider-level covariates to account for potential confounders and also to identify whether there is heterogeneity of the treatment effect (see below). The proposed models are outlined here. We will test both fixed effects and random effects.¹³⁹ (IR-3):

Primary Outcome: Model 1: Hierarchical Linear Model (Longitudinal Analysis)

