Question: Which communication strategy used during the clinical encounter is more effective in reducing pain interference over time for patients with chronic pain who were taking opioids at baseline?

Dependent variable: Pain interference as measured by PROMIS Pain Interference Score (T-Score, Continuous)

Independent variable: Comparator received, CDS vs. PEAT (Dichotomous)

Potential Covariates: Age, gender, race, ethnicity, mental health comorbidities, chronic pain diagnosis, use of other pain medications (neuropathic pain medications, NSAIDS, antidepressants), benzodiazepine use, number of office visits during intervention period, baseline HRQOL, encounter month, physician years of practice, physician gender, employment, SES.

Moderator Analyses: We will use statistical interactions examining the moderating effects of patient age, race, ethnicity, mental health comorbidities, chronic pain diagnosis, physician years of practice and physician gender on the relationship between comparator and pain interference.

Mediation Analyses: We will test whether confidence in decision and satisfaction with communication as measured by COMRADE Scores mediates the relationship between the comparator used and the pain interference outcomes.

Primary Outcome: Model 2: Hierarchical Linear Model (Longitudinal Analysis)

Question: Which communication strategy used during the clinical encounter is more effective in improving how satisfied patients feel over time after communicating with their physician about chronic pain treatment risks and benefits?

Dependent variable: CG-CAHPS

Independent variable: Comparator received, CDS vs. PEAT (Dichotomous)

Potential Covariates: Age, gender, race, ethnicity, educational level, mental health comorbidities, chronic pain diagnosis, use of other prescribed pain medications (neuropathic pain medications, NSAIDS, antidepressants) benzodiazepine use, number of office visits during intervention period, baseline HRQOL, encounter month, physician years of practice, physician gender, employment, SES.

Subgroup Analyses: We will use statistical interactions examining the moderating effects of patient age, race, ethnicity, education level, mental health comorbidities, chronic pain diagnosis; and physician years of practice and gender on the relationship between comparator and pain interference.

Secondary Outcome: Model 3: Hierarchical Linear Model

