Question: Which communication strategy used during the clinical encounter is more effective in improving patient's Health Related Quality of Life over time?

Dependent variable: PROMIS Physical Function, PROMIS Depression, and PROMIS Pain Interference Scores (T-Scored, Continuous)

Independent variable: Comparator received, CDS vs. PEAT (Dichotomous). **Potential Covariates:** Same as Model 2.

Secondary Outcome: Model 4: Hierarchical Generalized Linear Model

Question: Which communication strategy used during the clinical encounter is more effective in reducing opioid prescriptions of more than 90 Morphine Milligram Equivalents (MME) over time?

Dependent variable: Opioid Prescription over 90MME (Dichotomous)

Independent variable: Comparator received, CDS vs. PEAT (Dichotomous). **Potential Covariates:** Same as Model 2.

Other Analyses: We will also perform a differences-in-differences analysis at the beginning and the end of the intervention to determine which strategy resulted in greater reduction in high-risk prescriptions.

Secondary Outcome: Model 5: Hierarchical Generalized Linear Model

Question: Which communication strategy used during the clinical encounter is more effective in reducing co-prescriptions of opioids and benzodiazepines over time?

Dependent variable: Opioids and Benzodiazepines Co-Prescribed (Dichotomous)

Independent variable: Comparator received, CDS vs. PEAT (Dichotomous). **Potential Covariates:** Same as Model 2.

Other Analyses: We will also perform a differences-in-differences analysis at the beginning and the end of the intervention to determine which strategy resulted in greater reduction in high-risk prescriptions.

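### Model 5 may adjust opioid-benzodiazepine co-prescribing for undated benzodiazepine use, a component of its own outcome; if measured on study, the total arm effect is no longer estimated

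*Combined protocol and SAP*

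**What the plan says.** Section E5.b defines Model 5 as a hierarchical generalized linear model for a secondary outcome: "Dependent variable: Opioids and Benzodiazepines Co-Prescribed (Dichotomous". Its covariate entry reads "Potential Covariates: Same as Model 2". The Model 2 list includes the run "benzodiazepine use, number of office visits during intervention period, baseline HRQOL, encounter month". In that run one item is marked as baseline (HRQOL), one as counted on study (office visits), and benzodiazepine use carries no time point. Models 3 and 4 borrow the same list. Model 1 has its own list with the same undated drug items.

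On how covariates are used and chosen, E5.b says "We will adjust for patient- and provider-level covariates to account for potential confounders". E5.a describes tests of differences between the two arms and continues: "using these bivariate analyses, we will identify covariates and patient- and physician-level moderators to use in the regression models". The Patient Partner is also consulted on the final set.

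The Description of Comparators says of the third CDS alert: "This alert is triggered whenever an order for a benzodiazepine is entered in the setting of a preexisting opioid prescription, or vice versa". It says that the PEAT materials "include information about opioids along with alternatives to opioids, including nonsteroidal anti-inflammatory drugs (NSAIDs), aspirin and acetaminophen".

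For the Model 5 outcome, E5.b also plans a difference-in-differences analysis between the beginning and end of the intervention. No covariates are stated for it.

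**The concern.** A co-prescription requires both an opioid and a benzodiazepine. Putting benzodiazepine use on the right-hand side puts half of the outcome there. If that variable is recorded after the intervention starts, it is also something the CDS arm is designed to change, because alert 3 can fire on a benzodiazepine order. Conditioning on it blocks that route.

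Co-prescribing is one of the two Aim 3 measures. Model 5 could show little or no difference when one strategy does reduce co-prescribing, or give an odds ratio that answers a different question. A milder form of the same timing gap affects Models 1 to 4: non-opioid drugs taken during the study may be one way in which an arm affects pain interference or quality of life.

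**Working it through.** The plan gives no effect size, event rate or power figure for Model 5. Its only sample-size calculation is for PROMIS Pain Interference, so there is no stated figure to reproduce. All rates below are assumptions, except the 32% reduction used in step 4.

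**1. Structure.** Let B be benzodiazepine use and O be opioid prescription, both in the outcome window. The outcome is Y = B × O.
- If B = 0, then Y = 0 for every patient. The coefficient of B has no finite estimate (separation), and non-users contribute nothing to the arm comparison.
- If B = 1, then Y = O. The arm coefficient compares opioid continuation among benzodiazepine users.

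**2. Effect only through benzodiazepines.** Assume opioid continuation of 70% in both arms and benzodiazepine use of 30% versus 20%.
- Co-prescription: 0.30 × 0.70 = 0.21 and 0.20 × 0.70 = 0.14.
- Unadjusted OR = (0.14/0.86) / (0.21/0.79) = 0.61.
- OR among users = (0.70/0.30) / (0.70/0.30) = 1.0.
- With 25% in place of 20%: 0.25 × 0.70 = 0.175, and the unadjusted OR = (0.175/0.825) / (0.21/0.79) = 0.80. Among users it is again 1.0.

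**3. Effect only through opioids.** Assume benzodiazepine use of 30% in both arms and opioid continuation of 70% versus 60%.
- Co-prescription: 0.21 and 0.30 × 0.60 = 0.18.
- Unadjusted OR = (0.18/0.82) / (0.21/0.79) = 0.83.
- OR among users = (0.60/0.40) / (0.70/0.30) = 0.64.

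The effect is not lost here, but it is an effect on opioid continuation among users, on a different scale.

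**4. Simulation at the plan's size.** This used 960 patients, 80 providers, 300 runs per scenario and cluster-robust standard errors. No provider effect was simulated, so the power figures are only illustrative. Assumptions: 30% baseline benzodiazepine use; 85% still on opioids; in the PEAT arm 10% stop and 5% start a benzodiazepine; CDS acts only through benzodiazepines, with a 32% relative reduction. The 32% is borrowed from the benzodiazepine pilot in patients aged 65 and older cited in the plan. Co-prescription is then 26.0% (PEAT) versus 17.5% (CDS).

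| Benzodiazepine covariate in Model 5 | OR | Share of runs with p < 0.05 |
|---|---|---|
| None | 0.61 | 92% |
| Baseline use | 0.39 | 99% |
| Concurrent use | 1.02 | 3% |

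The first two odds ratios differ because one is conditional on a strong predictor; both are legitimate targets. Over baseline use of 15% to 45% and reductions of 20% to 50%, concurrent adjustment gives ORs of 0.95 to 1.04 with 3% to 6% rejections. Baseline adjustment gives ORs of 0.21 to 0.61 with power of 42% to 100%. In 200,000 simulated patients there were no events among non-users.

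**5. Mixed route.** Suppose CDS lowers benzodiazepine use by 16% in relative terms and opioid continuation from 85% to 0.85 × 0.81 = 69%. The OR is 0.61 with no benzodiazepine covariate and 0.39 with concurrent use. The opioid part survives; the benzodiazepine part does not.

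**6. Selection rule.** Under E5.a, covariates are identified from bivariate comparisons of the arms. An on-study benzodiazepine variable differs between arms when the intervention changes benzodiazepine prescribing. It is therefore more likely to enter Model 5 in the situation where it does most damage.

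**The case against.** The case on the other side has five parts.

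- **The covariates are only potential.** This stands: the plan permits the adjustment but does not commit to it. The selection rule in step 6 weakens the reassurance.
- **The term may mean baseline use.** This also stands as a possibility. E4.e extracts treatment history at enrolment, E5.b speaks of confounders, and the list marks its on-study item explicitly. Under this reading the adjustment is harmless and adds precision. But nothing ties the covariate to baseline, and the two readings give 0.39 and 1.02 in the main simulated scenario. Separation might be noticed during data exploration, but the plan does not say what would then be done.
- **A difference-in-differences analysis is planned for the same outcome.** It is a partial safeguard, so Aim 3 does not rest on Model 5 alone. It does not correct Model 5.
- **The complete loss is built into the assumptions.** Correct. A reader might infer that the whole effect would vanish because alert 3 works mainly by stopping benzodiazepine orders. The documents do not apportion the effect: alert 3 also fires in the reverse order, and alert 1 concerns opioid orders. Step 3 shows the opposite case.
- **The extension to Models 1 to 4 is not quantified.** Correct. A reader might infer that the primary pain-interference comparison is biased, but this has not been shown. The same timing ambiguity applies, aspirin and acetaminophen are not named in the covariate lists, and the Model 2 list covers only prescribed pain drugs.

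**Conclusion.** The point holds as a should-fix for a secondary outcome. Model 5 allows a component of its own outcome as a covariate without saying when it is measured. If it is measured during the study, the model stops estimating the total arm effect on co-prescribing. The part acting through benzodiazepine prescribing is removed (0.61 to 1.0, or 0.80 to 1.0, under the assumptions of step 2). The part acting through opioids remains on another scale (0.83 to 0.64 under step 3). Complete loss requires both on-study measurement in the outcome window and an effect that runs only through benzodiazepines; the documents establish neither.

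It would go too far to say that Model 5 will adjust for on-study use, or that Aim 3 cannot be answered. For Models 1 to 4 the point is precautionary.

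**What to change.** - **Model 5:** remove benzodiazepine use from the covariates and adjust for pre-intervention co-prescription status. This keeps the total effect as the target, and a strong pre-intervention predictor should add precision even if baseline use was what the authors meant.
- **Models 1 to 4:** as a precaution, define benzodiazepine use and other pain-medication use from a fixed window before the intervention starts. The milestone schedule has enrolment running to 12/31/2018, after the 1/1/2018 intervention start, so tie the window to the intervention start and not to each patient's entry.
- **Reporting:** present on-study use of these drugs by arm as a descriptive result, not as a covariate.
- **Difference-in-differences analysis:** state its covariates and apply the same timing rule.

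The cost is wording in the covariate lists. The schedule starts pharmacy data collection on 8/1/2017, before the intervention, and treatment history comes from the EHR at enrolment, so the baseline values should be available without new data collection.

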E4.d. Recruitment Procedures (PC-2). Patients meeting inclusion criteria who are managed by one of the 80 participating PCPs at the Cedars-Sinai Medical Network will be auto-enrolled in the study. Patients will receive a written notification via mail of their inclusion in the study and at that time they will be told about the study details, including research procedures and requirements for follow-up, as well as the risks and benefits of study participation. At this time, patients will have the opportunity to actively opt out of receiving the education materials (if they are randomized to PEAT arm). Patients who do not opt out will receive education materials and their care will proceed as usual. Patients who are passively enrolled will receive the study questionnaires via REDCap. We estimate that out of the 4,000 patients eligible for the study (calculated from a quality improvement project based on claims data), approximately 30% will complete all of the questionnaires, which is in line with our sample size calculations. Once the patients complete monthly questionnaires, we will provide a \$5 gift card for filling out the enrollment survey. We have budgeted \$25 per patient as

a financial incentive for completing the questionnaires (Appendix I, **Table 1 for Recruitment Plan** and **Table 2 for Passive Enrollment Estimates**).

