b. Statistical Methods to Handle Missing Data and Sensitivity Analyses. If the data is not missing at random, we will use multiple imputation techniques to impute missing data for respondents (MD-2). We plan on using the *mi impute mvn* command in Stata and will generate 20 datasets compatible with the regressions planned for the final analyses. To insure that the imputation has proceeded as expected, we will visually inspect parameters from successive iterations of the model to determine if they have reached a stationary distribution. We will conduct sensitivity analyses with the dataset that includes imputed data as well as with a dataset that does not include imputed data to determine the effect of the multiple imputation and plan on reporting both results. These precautions will serve to identify autocorrelation in the imputed data and allow for proper maintenance of uncertainty in imputed values (MD-3).

c. Reporting Reasons for Dropout and Missing Data. We will drop data from patients who do not have any visits with their PCP during the intervention period or are lost to follow-up, but will compare descriptive statistics for these patients to patients with at least one visit to their PCP for sensitivity analysis (MD-4, MD-5).

E9. Project Milestones and Timeline.

During the first 3-6 months of the study project, we will train the project staff, refine the study protocol, develop the data dictionaries, and obtain IRB approval. We will hold monthly meetings with our patient partners to finalize the study design and discuss issues related to IRB approval. In Year 1, Q4, we will passively enroll eligible patients in the two study arms. In the 4 weeks before the intervention period, we will send baseline questionnaires via REDCap. In Year 2, we will begin the intervention. We will conduct weekly reports from our EHR data warehouse to determine enrolled patient visits. Enrolled patients will be sent CG-CAHPS survey one day after each primary care visit. Enrolled patients will also receive the PROMIS questionnaires once a month. We will perform monthly checks to assess the completeness of data to minimize missing data and will complete one set of interim data analyses in Year 2 to assess whether there are any issues with missing data. Full data analysis will

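### Models 4 and 5 inherit baseline HRQOL as a potential covariate, so a standard fit could drop questionnaire non-responders from prescribing outcomes that need no patient response

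*Combined protocol and SAP*

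**What the plan says.** Section E5.b defines two prescribing models for Aim 3. Model 4 takes an opioid prescription over 90 MME as its outcome. Model 5 is specified as "Dependent variable: Opioids and Benzodiazepines Co-Prescribed (Dichotomous". Both give their potential covariates as "Same as Model 2", and the Model 2 list includes "number of office visits during intervention period, baseline HRQOL, encounter month".

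- **Source of the outcomes.** Section E6.d, item 4, takes opioid prescriptions from pharmaceutical claims linked to the EHR. Milestone B11 in Attachment C-R has pharmacy data pulled for passively enrolled patients. Neither depends on a questionnaire.
- **Source of baseline HRQOL.** Section E9 sends baseline questionnaires by REDCap in the four weeks before the intervention. Section E6.d, item 2, adds passive collection of some PROMIS measures from routine care, without giving their coverage.
- **Expected response.** Section E4.d counts 4,000 eligible patients, auto-enrolled under 80 physicians, of whom "approximately 30% will complete all of the questionnaires".
- **Missing data.** Section E7.b says that if data are not missing at random, "we will use multiple imputation techniques to impute missing data for respondents". Section E7.c drops patients with no visit to their primary care physician and those lost to follow-up.
- **Analysis set.** None is named for Models 4 and 5.

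**The concern.** The covariate list was written for a survey outcome. In Model 2 a patient who does not answer has no outcome either, so adjusting for a questionnaire score costs little extra. In Models 4 and 5 the outcome is known whether or not the patient answers, and the covariate becomes the thing that decides who is analysed.

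Two things are at stake. The first is precision, because patients with a known outcome would be left out. The second matters more. Response comes after allocation, so the analysed set would be selected on something that happens after randomisation. Section E7.a itself recognises a possible link between not completing surveys, not using the educational tools and poorer HRQOL. Section D2 says that a stable eligible population is critical for the Aim 3 rates, which points to an analysis of the eligible population and not of those who answer.

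**Working it through.** **1. Does a non-responder stay in the model?** A regression needs every covariate for every row, so a patient without baseline HRQOL drops out unless the value is imputed. The maximum likelihood statement in E7.a concerns the hierarchical linear model. Models 4 and 5 are generalized linear models, and likelihood estimation conditional on covariates does not in any case recover a missing covariate. The imputation in E7.b is conditional and limited to respondents. No stated rule keeps a non-responder in.

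**2. Is response before or after allocation?** Milestone B9 completes randomisation on 7/30/2017, and milestone B12 starts baseline questionnaires on 8/1/2017. Section E9 places them in the four weeks before the intervention, which milestone C1 starts on 1/1/2018. On either timing, response follows randomisation.

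**3. How many patients?** 0.30 × 4,000 = 1,200 complete every questionnaire, and 4,000 − 1,200 = 2,800 (70%) do not. A baseline covariate needs only the baseline score, and that response rate is not given. The number with baseline HRQOL therefore lies between 1,200 and 4,000, and 70% is the largest loss, before the exclusion for no visit.

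**4. What does it cost in precision?** The plan gives no sample size for Models 4 and 5, so there is no figure to reproduce. Inputs are 80 physicians (E4.d), the ICC of 0.02 (E5.c, set for PROMIS Pain Interference) and, as an assumption for prescribing, an ICC of 0.10.

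Design effect = 1 + (N/80 − 1) × ICC. Effective N = N / design effect. SE ratio = √(effective N for 4,000 / effective N for the subset).

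| ICC | N analysed | Design effect | Effective N | SE ratio |
|---|---|---|---|---|
| 0.02 | 4,000 | 1 + 49 × 0.02 = 1.98 | 2,020 | 1 |
| 0.02 | 2,000 (50%) | 1 + 24 × 0.02 = 1.48 | 1,351 | 1.22 |
| 0.02 | 1,200 (30%) | 1 + 14 × 0.02 = 1.28 | 938 | 1.47 |
| 0.10 | 4,000 | 1 + 49 × 0.10 = 5.90 | 678 | 1 |
| 0.10 | 2,000 (50%) | 1 + 24 × 0.10 = 3.40 | 588 | 1.07 |
| 0.10 | 1,200 (30%) | 1 + 14 × 0.10 = 2.40 | 500 | 1.16 |

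**5. As a detectable difference.** This uses the usual two-proportion formula on effective N, two-sided 0.05 and 80% power, with an assumed comparison-arm rate of 10%. At ICC 0.02 the detectable reduction is 3.4 points with 4,000 patients and 4.8 points with 1,200. At ICC 0.10 it is 5.6 and 6.3 points. With an assumed rate of 30%, the pairs are 5.5 and 8.0, and 9.3 and 10.8.

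**The case against.** The strongest objection is that the plan nowhere restricts Aim 3 to responders. A reader might infer that Models 4 and 5 are to be run in the 30% who answer, and the documents do not say that. The covariates are called potential, and section E5.a lets bivariate comparisons and the patient partner decide which are used. Item 10 of the PRECIS list plans an ITT analysis. E5.b adds difference-in-differences analyses of both outcomes with no covariate list. This stands, and it makes the loss conditional. It does not remove it: neither the ITT mention nor the difference-in-differences text says how patients without a covariate are handled. Leaving the choice to bivariate screening also means that the analysed population could depend on which covariates are picked.

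Other limits also stand:

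- The 30% is for all questionnaires, so it is a floor for baseline response.
- Routine-care PROMIS scores may fill some gaps.
- A reader might count education, employment and SES as further questionnaire items because section E4.e does not list them for EHR extraction. That list also omits age and gender, so it is not exhaustive, and Appendix I, Table 3, which gives the sources, is not in the text reviewed. The point rests on baseline HRQOL alone.
- A reader might expect the extra PEAT contact to drive baseline response. PEAT materials go out two days before a visit (E4.c), mostly after baseline, so that mechanism is not shown.
- The ICC of 0.02 was not chosen for prescribing, and with a larger one most of the precision loss disappears.
- Milestone B10 gives passive enrolment as 960, so the 4,000 is itself an assumption about who has prescribing data.

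**Conclusion.** The point holds as a conditional one. If baseline HRQOL is retained in Models 4 and 5, a standard fit drops patients whose prescribing outcome is known, and nothing in the plan prevents this. The loss is at most 70% of about 4,000 patients, and smaller by an amount that the documents do not let us calculate if baseline response or routine-care PROMIS coverage is higher. At the 30% floor the SE grows by a factor of 1.16 to 1.47 over the ICC range of 0.10 to 0.02, with 80 physicians and equal cluster sizes.

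The selection problem does not depend on the ICC. Whatever the precision loss, the comparison would be conditioned on a response that follows allocation. The size of any resulting bias cannot be derived from the documents, and differential response by arm is a risk, not a finding. Since these are secondary outcomes and the remedy uses data already planned, this is a worthwhile correction to the SAP and not a flaw in the trial's design.

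**What to change.** 1. Replace the inherited list in Models 4 and 5 with one of their own, limited to pre-intervention data available for every enrolled patient: age, gender, race/ethnicity, mental-health and pain diagnoses, baseline prescribing, and physician factors. Fix the list in advance, not by bivariate screening.
2. Name the Aim 3 analysis set: all auto-enrolled patients who meet the plan's own visit criterion, analysed by randomised arm, regardless of questionnaire response. State the expected number, and so settle whether it is about 4,000 or 960.
3. Keep the model with baseline HRQOL as a sensitivity analysis, and report how many patients in each arm it omits.

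A separate list would also remove two other awkward inherited terms, which are distinct issues: benzodiazepine use, a component of the Model 5 outcome, and the number of office visits during the intervention, which is measured after randomisation.

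The cost is SAP wording, with no new data collection. The downside is that the main Aim 3 model no longer adjusts for baseline HRQOL.
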